Pushing Qiaogong (推橋弓)	Anterior cervical sternocleidomastoid muscle	Apply massage oil to the subject's sternocleidomastoid muscles in the front neck area, then use the pads of the index and middle fingers, or the middle finger alone, move swiftly downwards from the back of the ear, along the sternocleidomastoid muscle. The movement should be light and cause no discomfort to the subject. Repeat 50 times on each side.
Grasping Jianjing (拿肩井)	Acupoint GB21 (Jianjing)	Place a thin towel on the subject's shoulder, then use the thumbs and index/middle fingers of both hands to lift and grasp the shoulder muscle of both shoulders with appropriate force. Repeat 5 times.
Grasping Hegu (拿合谷)	Acupoint LI4 (Hegu)	Use the thumb and index/middle fingers of one hand to lift and grasp the acupoint LI4 (Hegu) of both hands of the subject with appropriate force. Repeat 5 times.

Table 3. Standard protocol items: recommendations for intervention trials (SPIRIT) schedule of enrollment, interventions, and assessment.

Timepoint	Study Period				
	Enrolment	Allocation	Post-allocation		
			$t_1$ Start	$t_2$ 6-week	$t_3$ 12-week
Enrolment					
	Eligibility screen	X			
	Informed consent	X			
	Demographics	X			
	Allocation		X		
Interventions					
	Intervention: CAT		◀	▶	
	Intervention: CAE		◀	▶	
	Control: routine care		◀	▶	
Assessments					
	MoCA	X		X	X
	Digit Span	X		X	X
	MBI	X		X	X
	VAS	X		X	X
	GDS	X		X	X
	ISI	X		X	X

Abbreviations: t, timepoint; CAT, comprehensive acupuncture therapy; CAE, Comfy Acupressure for the Elderly; MoCA, Montreal Cognitive Assessment; MBI, Modified Bathel Index; VAS, Visual Analogue Scale; GDS, Geriatric Depression Scale; ISI, Insomnia Severity Index.

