- (b) to determine whether other symptoms (e.g., functional independence, pain, depression, and sleep disorder) in the treatment group improve more than in the control group; and
- (c) to investigate whether acupuncture or acupressure is safe for the elderly with cognitive impairment or dementia.

Patient population

Elderly patients with cognitive impairment or dementia are eligible for enrolment.

Inclusion criteria

Subjects will be eligible for this study if they:

- (a) are aged 65 years or above;

- (b) have a clinical diagnosis of any type of dementia or met the criteria of major and mild neurocognitive disorder based on the Fifth Edition of the Diagnostic and Statistical Manual of Mental Disorders (DSM-5);¹ and
- (c) have mild to moderate dementia at a stage of 3 to 5 on the Global Deterioration Scale.²

Exclusion criteria

Subjects will be excluded if they:

- (a) have the severity of dementia with a stage below 3 or above 5 on the Global Deterioration Scale;
- (b) have severe skin lesions on acupuncture and acupressure areas;
- (c) have a significant bleeding tendency;
- (d) have a heart pacemaker or implantable cardioverter defibrillator;
- (e) are currently receiving acupressure as a regular therapy;
- (f) have had surgery on the head or neck; or
- (g) are currently receiving anti-coagulant treatment.

Randomization, central allocation and blindness

One independent research assistant will be in charge of randomization and central allocation as the central coordinator. After confirmation of patients' eligibility and completion of the baseline assessment, participants will be randomly assigned to CAT, CAE, CAT+CAE, or routine care groups in a ratio of 1:1:1:1. Random codes were produced in advance using simple, complete, non-sequential numbers, with a block of 4, 8 and 12, through a random allocation software at <http://mahmoodsaghaei.tripod.com/Softwares/randalloc.html>. Randomization information will be sealed in sequentially numbered opaque envelopes.

Central allocation will be conducted, i.e., site investigators who are responsible for subjects' eligibility will obtain the opaque envelope from the central coordinator for an eligible subject who will be allocated to one of the four groups. Each envelope will be opened by acupuncturists after the participant completes the baseline assessment. Clinical assessors and data analysts will be blind to patients' treatment.

Intervention

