Our recent study showed that CAT treatment for 8 weeks produced a 2.3 ± 2.8 (SD) score greater improvement than control (minimum acupuncture stimulation, MAS) on MoCA in patients with poststroke cognitive impairment.¹³ One similar trial has reported that acupuncture treatment alone for 3 months yielded a 1.9 ± 4.1 greater improvement than nimodipine, a commonly used anti-hypertension drug, on MoCA in patients with poststroke cognitive impairment.¹⁴ Based on these two trials, we expect that CAT could yield an average 2.1 [$(2.3+1.9)/2 = 2.1$] score greater improvement on MoCA than routine care, with an average standard deviation (SD) equal to a 1.7-fold of mean difference [$(2.8/2.3 + 4.1/1.9)/2 = 1.7$], i.e., $SD = 1.7 \times 2.1 = 3.6$. The following formula is then used to further calculate the sample size:

$$n = \frac{2}{(M/SD)^2} \times C_{p,\text{power}}$$

where n is the number of subjects required in each arm and M is the mean difference that is equal to 2.1. SD is the standard deviation that is 3.6. $C_{p,\text{power}}$ is equal to 7.9 when the two-tailed level of α and power ($1-\beta$) are set at 0.05 and 80%, respectively. It requires 62 subjects per arm, with an assumed dropout rate of 25%. We propose to recruit a total of 248 subjects ($n = 62$ per arm for 4 arms).

Data processing and analysis

General principles

One biostatistician who is blinded to interventions will be responsible for statistical analysis. The analysis will be carried out on the intention-to-treat (ITT) population. For all primary and secondary outcomes, two-tailed P-values will be reported in addition to confidence intervals. The nominal level of statistical significance (α) will be 5%. The analysis and reporting of the results will follow the Consolidated Standards of Reporting Trials (CONSORT) guidelines.

Analysis software

All analyses will be performed using R Studio version 4.0.0 or later.

Analysis Populations

All analyses will be carried out on the intention-to-treat (ITT) population, for which participants have been randomized, completed the baseline assessment regardless of protocol compliance.¹⁵ The flow of patients throughout the trial will be shown using a CONSORT diagram (Figure 1).

Demographic characteristics and baseline comparisons

Baseline comparisons will be tabulated for the following variables (Proposed Table 1):

- (a) Age
- (b) Gender (Categories: male / female)

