- (c) severity of dementia (mild cognitive decline [Stage 3], moderate cognitive decline [Stage 4], moderately severe cognitive decline [Stage 5])

Secondary outcomes

A linear mixed-effect model will be applied to compare the secondary outcomes, including changes in scores of the Digit span test (DSF and DSR), MBI, VAS, GDS and ISI, with time (baseline, week 6, and week 12) and group (CAT, CAE, CAT+CAE, and routine care) as categorical fixed factors and random intercepts within a scaled identity covariance matrix. Gender, age, baseline MoCA score, and baseline medication will serve as covariates.

Pairwise comparisons will be further carried out to examine between-group differences. Two-tailed P-values will be reported in addition to confidence intervals ([Proposed Tables 2 and 3](#)).

Safety outcomes

AEs related to treatment will be tabulated by treatment group without statistical tests or confidence intervals ([Proposed Table 4](#)).

All AEs that occurred throughout the trial will be tabulated by treatment group and AE category (mild, moderate, severe, life-threatening, or death). Chi-square test or Fisher's exact test will be used to detect differences between the four groups ([Proposed Table 5](#)).

Details of serious AEs and death cases will be summarized and listed in a separate table.

Interim analysis

No interim outcome analyses were done prior to the completion of the study to avoid assessment bias.

Missing data

A linear mixed-effect model will be conducted for all analyses of primary and secondary outcomes without imputation of missing data.¹⁶

Proposed Tables

Table 1. Baseline characteristics

Characteristic	CAT (n=62)	CAE (n=62)	CAT+CAE (n=62)	Routine care (n=62)	Total (n=248)	P value
Age, years *	XX ± XX	XX ± XX	XX ± XX	XX ± XX	XX ± XX	XX
Gender (Female) †	XX (XX)	XX (XX)	XX (XX)	XX (XX)	XX (XX)	XX
Marital status †						XX
Married or living with partner	XX (XX)	XX (XX)	XX (XX)	XX (XX)	XX (XX)	
Single, separated, divorced, or widowed	XX (XX)	XX (XX)	XX (XX)	XX (XX)	XX (XX)	
Education level †						XX
Uneducated	XX (XX)	XX (XX)	XX (XX)	XX (XX)	XX (XX)	
Primary or below	XX (XX)	XX (XX)	XX (XX)	XX (XX)	XX (XX)	
Lower Secondary	XX (XX)	XX (XX)	XX (XX)	XX (XX)	XX (XX)	
Upper Secondary	XX (XX)	XX (XX)	XX (XX)	XX (XX)	XX (XX)	
University or above	XX (XX)	XX (XX)	XX (XX)	XX (XX)	XX (XX)	
Past occupation †						XX
Managers and administrators	XX (XX)	XX (XX)	XX (XX)	XX (XX)	XX (XX)	

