‡ P value was calculated using a mixed-effects model with baseline adjustment to illustrate pre- and post-treatment within-group differences. Those which statistical differences $p<0.05$ reached significance level are indicated in bold font

Table 4. Adverse events related to treatment, n (%)^{*}

Adverse event	CAT (n = 62)	CAE (n = 62)	CAT+CAE (n = 62)
Bleeding at the site of needling	XX (XX)	XX (XX)	XX (XX)
Hematoma around the site of needling	XX (XX)	XX (XX)	XX (XX)
Dizziness after treatment	XX (XX)	XX (XX)	XX (XX)
Headache after treatment	XX (XX)	XX (XX)	XX (XX)
Localized pain	XX (XX)	XX (XX)	XX (XX)
Needle phobia	XX (XX)	XX (XX)	XX (XX)

Abbreviations: CAT, comprehensive acupuncture therapy; CAE, Comfy Acupressure for the Elderly.

* Data was expressed as number of patients (%).

Table 5. Reported adverse events in different categories, n (%)^{*}

Adverse Event Category	CAT (n=62)	CAE (n=62)	CAT+CAE (n=62)	Routine care (n=62)	P-value*
Any	XX (XX)	XX (XX)	XX (XX)	XX (XX)	XX
Mild	XX (XX)	XX (XX)	XX (XX)	XX (XX)	XX
Moderate	XX (XX)	XX (XX)	XX (XX)	XX (XX)	XX
Severe	XX (XX)	XX (XX)	XX (XX)	XX (XX)	XX
Life-threatening	XX (XX)	XX (XX)	XX (XX)	XX (XX)	XX
Death	XX (XX)	XX (XX)	XX (XX)	XX (XX)	XX

Abbreviations: CAT, comprehensive acupuncture therapy; CAE, Comfy Acupressure for the Elderly.

* Data was expressed as number of patients (%). Those which statistical differences $p < 0.05$ reached significance level are indicated in bold font.

[figure not shown]

Figure 1. CONSORT Flowchart

References

1. American Psychiatric Pub. Diagnostic and Statistical Manual of Mental Disorders (DSM-5®). American Psychiatric Pub; 2013.

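### Treatment-related adverse events are tabulated without confidence intervals or an overall row, so the plan does not show how much risk an arm of 62 can rule out

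*SAP*

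**What the plan says.** The third aim in the SAP's Hypothesis and aims section is "to investigate whether acupuncture or acupressure is safe for the elderly with cognitive impairment or dementia", and hypothesis (a) in the same section includes safety.

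The Safety outcomes part of the SAP's analysis section plans three outputs:

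- **Table 4, treatment-related events.** The rule is "AEs related to treatment will be tabulated by treatment group without statistical tests or confidence intervals". The shell has columns for CAT, CAE and CAT+CAE, each headed n = 62, and counts patients. Its six rows are "Bleeding at the site of needling", hematoma at the needling site, dizziness, headache, localized pain and needle phobia.
- **Table 5, all events.** Four arms, an overall row and five severity rows, with a Chi-square or Fisher test.
- **A separate listing** of serious events and deaths.

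The SAP's General principles promise confidence intervals for all primary and secondary outcomes. No safety output is given one.

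**The concern.** Leaving significance tests off sparse adverse event counts is defensible. Leaving intervals off is a separate decision, and the SAP gives no reason for it. The interval is what tells a reader how large a risk is still compatible with few or no events in 62 patients.

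The shell has two further gaps.

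- **No overall row for related events.** The proportion of patients with at least one related event is the most direct summary for the safety aim, and no planned output gives it.
- **Three CAE cells that can only be zero.** CAE is massage and pressure without needles, but the shell gives it ordinary count cells for needling-site bleeding, needling-site hematoma and needle phobia. A zero there reflects absence of exposure and is not evidence of safety. CAE also has contacts of its own in Protocol Table 2: massage oil on the skin, kneading of neck and shoulder, and strokes along the front of the neck, for which the table says "The movement should be light and cause no discomfort to the subject. Repeat 50 times on each side". Pain from these would fit the localized pain row. A skin reaction would fit none of the six.

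At stake is how precisely the trial can answer its safety aim. The efficacy analysis is not affected.

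**Working it through.** **Inputs.** The SAP's Sample size determination gives M = 2.1, SD = 3.6 and C = 7.9 (two-tailed alpha and power "are set at 0.05 and 80%, respectively"), and states "It requires 62 subjects per arm, with an assumed dropout rate of 25" per cent. Allocation is 1:1:1:1. Table 4 counts patients, so each cell is a binomial proportion out of 62.

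**The plan's own figure.** n = 2/(2.1/3.6)² × 7.9 = 46.43 evaluable patients per arm, and 46.43/(1 − 0.25) = 61.9, that is 62. The denominator reproduces. The documents state no precision or detectable rate for adverse events.

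**Upper limit for a zero cell.** The exact (Clopper-Pearson) limit is 1 − 0.025^(1/n) two-sided 95%, and 1 − 0.05^(1/n) one-sided 95%.

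| Patients observed | Two-sided 95% | One-sided 95% |
|---|---|---|
| 62 | 5.8% | 4.7% |
| 46 (about 62 × 0.75) | 7.7% | 6.3% |
| 124 (two arms pooled) | 2.9% | 2.4% |

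Two checks on 0/62: the Wilson upper limit is 5.8%, and the rule of three gives 3/62 = 4.8%.

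**Small non-zero cells.** The exact two-sided 95% interval is 0.04% to 8.7% for 1/62, and 0.4% to 11.2% for 2/62.

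**How often a real risk leaves the cell empty.** P(0 of 62) = (1 − p)^62. For a true risk of 2% over the 12 weeks this is 0.98^62 = 29%; for 3% it is 0.97^62 = 15%.

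**Rows that cannot register a CAE event.** Three of six name needles or needling, which is half. The other three (dizziness, headache, localized pain) can occur with CAE.

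**Why the overall proportion cannot be recovered.** Rows count patients, and one patient may appear in several. For example, if two rows held 2 and 3 patients and the rest were empty, the number with any related event could be anything from 3 (full overlap) to 5 (none). A reader can work out an interval for a single row by hand, but not this summary.

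**The case against.** The strongest reply is that Table 4 is not the whole safety analysis. Table 5 has an overall row, covers all four arms including routine care, carries a test and is not built around needles, so a CAE event of any type counts there. Serious events and deaths are listed separately. This stands, and it rules out saying that the acupressure half of the aim rests on a list made for needles. It does not close the gap: Table 5 plans no intervals, is arranged by severity and does not separate related events.

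A second reply is that the shells are only proposed, and that the SAP text does not limit related events to six terms. Both documents require new or worsened events to be recorded with their relationship to the intervention. This also stands. A reader might infer that a related event outside the six rows would be dropped, but nothing says so. What remains is that the text and the shell should be aligned.

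A third is that nothing in the documents says an empty cell will be read as proof of safety. That is correct. Such a reading is a prediction about how results might be described, not a rule in the plan.

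A fourth is that the denominators are printed, so a reader could derive intervals. That holds for single rows only.

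**Conclusion.** The point holds as a minor improvement. For a stated aim, the SAP expressly excludes the measure of precision, and no planned output gives the proportion of patients with any related event. An empty cell with 62 observed cannot by itself exclude a risk of 5.8% (two-sided 95%), or 4.7% on a one-sided limit.

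These figures assume a count of zero, one count per patient and all 62 randomized patients observed; with about 46 observed, the two-sided limit is 7.7%. They do not apply to the needle-specific rows under CAE, where there is no exposure and no risk to bound.

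A reader might take the shell to be mostly about needling. It is not: half the rows are needle-specific, and it becomes a majority only if localized pain is counted as needling pain, which its label does not say. Data capture, the efficacy analyses and the comparison in Table 5 are untouched.

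**What to change.** In the SAP's Safety outcomes text, keep the exclusion of statistical tests for treatment-related events and replace the exclusion of intervals with exact 95% confidence intervals. In Table 4:

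1. State that every adverse event judged related is listed, so that the six rows are not a closed set.
2. Add rows for *any related AE* and *any serious related AE*, counted by patient, with exact intervals.
3. Mark the three needle-specific rows *not applicable* for CAE.
4. If arms are pooled to n = 124, restrict this to the needle-specific rows in CAT and CAT+CAE. Patients in CAT+CAE also receive acupressure, so pooling the dizziness, headache or localized pain rows as needling events would mix exposures.

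The cost is SAP wording and a table shell. Relationship to intervention is already to be recorded, so no new data or patient contact is needed. The downside is that the safety statement becomes more cautious.

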The GDS-15 consists of 15 questions in which subjects are asked to respond by answering yes or no in reference to how they felt over the past week. Of the 15 items, 5 items (question numbers 1, 5, 7, 11, 13) indicate depression when answered negatively, while the rest (question numbers 2, 3, 4, 6, 8, 9, 10, 12, 14, 15) indicate the presence of depression when answered positively. The GDS-15 score is interpreted as follows: normal (0-4), mild depression (5-8), moderate depression (9-11), and severe depression (12-15). GDS can be used in mild to moderately cognitively impaired older adults. ISI is a

validated 7-item scale to assess the severity of insomnia. The total score ranges from 0 to 28, with scores of 0-7 indicating no clinically significant insomnia, 8-14 indicating subthreshold insomnia, 15-21 indicating moderate insomnia, and 22-28 indicating severe insomnia. Depressive and sleep symptoms are investigated because elderly people with cognitive impairment often have comorbid emotional and sleep disorders. The benefits of acupuncture and acupressure for depression and insomnia have been confirmed in our previous studies.

(c) Adverse events: The severity of adverse events (AEs) will be assessed according to the Common Terminology Criteria for Adverse Events (CTCAE) v5.0 criteria. AEs will be systematically recorded, in which AEs that first appear in the study or worsen relative to the pre-study status will be recorded at each visit, including the date and time of onset, duration, severity, relationship to intervention, and action taken accordingly. All possible events will be independently evaluated by staff who do not assess treatment outcomes. The causality between treatment procedures and AEs will be assessed.

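### No planned table compares a non-serious adverse event type with routine care: the by-type table holds only treatment-related events in the active arms, and the all-event table shows severity only

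*SAP*

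**What the plan says.** Aim (c) of the SAP is "to investigate whether acupuncture or acupressure is safe for the elderly with cognitive impairment or dementia". The SAP's safety outcomes section plans three outputs.

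- **Table 4**, titled "Table 4. Adverse events related to treatment, n" (%), is the only shell with event types. Its six rows are needling-site bleeding, hematoma, dizziness, headache, localized pain and needle phobia. Its columns are CAT, CAE and CAT+CAE. The text says: "AEs related to treatment will be tabulated by treatment group without statistical tests or confidence intervals".
- **Table 5**, titled "Table 5. Reported adverse events in different categories, n" (%), has all four arms. The text says: "All AEs that occurred throughout the trial will be tabulated by treatment group and AE category (mild, moderate, severe, life-threatening, or death"). Its rows are Any and the five grades, each with a four-group chi-square or Fisher P value. No row names an event type.
- **Serious AEs and deaths** go to a separate table, for which no shell is given.

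On attribution, the Protocol (Assessment, part c) says: "The causality between treatment procedures and AEs will be assessed". It adds that events are evaluated independently by staff who do not assess treatment outcomes. Neither document gives a relatedness scale or a cut-off for entry to Table 4. Both documents have new or worsened AEs recorded whatever their cause, and the Protocol's assessment schedule extends recording to routine care.

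**The concern.** Bleeding or hematoma at a needling site needs no control column. Dizziness, headache and localized pain do, because they also occur without treatment in care-home residents aged 65 or over. For these rows Table 4 gives a count selected by judgement, with no background rate beside it. Table 5 has the background rate but merges every event type within a grade.

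A non-serious event type that rises under treatment but is judged unrelated would therefore appear only inside Table 5's pooled rows, where other events dilute it. If it is judged related, it appears in Table 4 with nothing to compare it with. At stake is the evidence behind any statement on aim (c). The efficacy analysis is not affected.

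**Working it through.** **1. Denominator.** The safety section states no figure of its own; its tables use 62 per arm. That number reproduces from the plan's inputs (M = 2.1, SD = 3.6, C = 7.9, dropout 25%): n = 2/(2.1/3.6)² × 7.9 = 46.4, and 46.4/0.75 = 61.9, so 62.

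**2. Coverage of the planned outputs.**

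| Output | Events | By type? | Routine care? |
|---|---|---|---|
| Table 4 | judged treatment-related | yes | no |
| Table 5 | all | no, severity only | yes |
| Serious AEs and deaths | serious and fatal | possibly (no shell) | not stated |

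For non-serious events, no row answers yes to both of the last two columns. The Protocol's data analysis section plans a test on AE incidence but gives no breakdown by type.

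**3. Size of the dilution (illustration).** The documents give no AE rates, so every rate here is an assumption. Let p0 be the risk of one event type in CAE and routine care, p1 its risk in CAT and CAT+CAE, and b the risk of any other AE, independent and equal across arms. The Any-row risk is 1 − (1 − p)(1 − b). For p0 = 5%, p1 = 20%, b = 30%:

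- without the excess: 1 − 0.95 × 0.70 = 33.5%
- with the excess: 1 − 0.80 × 0.70 = 44.0%

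A fourfold ratio becomes 44.0/33.5 = 1.3. Simulated power of the four-arm chi-square test at 5%, with 62 per arm:

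| p0 to p1 | By-type row | Any row, b = 30 / 50 / 70% | Any row, b = 10% |
|---|---|---|---|
| 5% to 15% | 59% | 14 / 9 / 7% | 29% |
| 5% to 20% | 89% | 26 / 15 / 9% | 58% |
| 10% to 25% | 76% | 26 / 15 / 9% | 51% |
| 5% to 10% | 20% | 7 / 6 / 5% | 11% |
| 10% to 20% | 43% | 13 / 9 / 7% | 25% |

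A single grade row behaves in the same way for a given background in that grade. With 46 per arm (62 × 0.75 = 46.5), by-type power for 5% to 15% falls from 59% to about 44%.

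**4. What an estimate would show.** The approximate 95% CI for a risk difference is d ± 1.96 × √[p0(1 − p0)/62 + p1(1 − p1)/62].

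- 20% vs 5%: 15 ± 1.96 × 5.8 = about 4 to 26 percentage points.
- 10% vs 5%: 5 ± 1.96 × 4.7 = about −4 to 14 percentage points.

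**The case against.** **Much of safety is covered elsewhere.** Serious events and deaths have a separate table. Pain is compared across all four arms at weeks 6 and 12 through the VAS with 95% CIs, although this may miss brief needling pain. This stands, and it confines the point to non-serious events, with pain only partly affected.

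**The power contrast depends on the assumed background.** This also stands. At 10% background, the Any row has 58% power for a rise from 5% to 20%. A grade row may have a lower background than Any. The figures illustrate the mechanism and do not predict what this trial would show.

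**A reader might infer that those judging causality must know the arm, because there is no sham.** The documents do not support that. Lack of a sham unblinds participants and therapists, but not necessarily an independent evaluator. The plan names blinding only for clinical assessors and data analysts and is silent on the staff who evaluate AEs. What can be said is that the safeguard is not stated.

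**A reader might infer that the added table would reveal a doubling.** It usually would not by a significance test: power is about 20% for 5% to 10% and 43% for 10% to 20%. What the table adds is a visible estimate with its interval.

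**A raw four-arm comparison would be unequal.** Under the Protocol's assessment schedule, active arms are asked at every treatment session (24 for CAT, 36 for CAE, up to 24 + 36 = 60 for the combination if given separately) and at assessments. Routine care is recorded only at baseline, week 6 and week 12. Restricting to common visits removes that inequality but loses brief reactions reported only at a session, such as "Dizziness after treatment". Neither version is sufficient alone.

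**Conclusion.** The gap is real and can be read directly from the table shells: as planned, no output sets a non-serious event type in the active arms against routine care. This rests on no assumed rate. Its possible cost does. With 62 per arm, both CAT-containing arms affected and 30–70% background, a rise from 5% to 15–20% would be picked up about 59–89% of the time on a by-type row and about 7–26% on the Any row. The contrast is smaller where the background is low.

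The documents do not show that attribution is biased, that serious harms would go unseen, or that a safety conclusion would be wrong. This is a worthwhile reporting change in support of aim (c), not a flaw in the trial's main analysis.

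**What to change.** - **Add one descriptive table:** all AEs regardless of judged relatedness, grouped by event type, for all four arms. Give number of patients (%) and the risk difference of each active arm vs routine care with 95% CI.
- **Show it in two versions side by side:** all recorded AEs, with a note on the unequal frequency of questioning; and AEs elicited at the visits common to all arms.
- **Keep Table 4** as a description of attributed events. State the relatedness scale, the cut-off for entry, and whether those judging causality know the arm.
- **Draw statements on aim (c)** from the all-cause table together with Table 5 and the serious AE table.

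Cost: no new data collection, but the entries must be grouped by type. The documents name CTCAE for severity only and list no coding by term or organ class. There will be more rows, to be read descriptively without multiplicity control.

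### SAP Table 5 tests each exact AE grade in its own row, and no planned comparison covers severe-or-worse AEs or any serious AE

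*SAP*

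**What the plan says.** The SAP (Hypothesis and aims) sets as its third aim "to investigate whether acupuncture or acupressure is safe for the elderly with cognitive impairment or dementia".

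The SAP's Safety outcomes section under Data processing and analysis plans three outputs:

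- Table 4, treatment-related events: "AEs related to treatment will be tabulated by treatment group without statistical tests or confidence intervals". It has no routine care column.
- Table 5, titled "Reported adverse events in different categories": "All AEs that occurred throughout the trial will be tabulated by treatment group and AE category (mild, moderate, severe, life-threatening, or death". Its rows are Any, Mild, Moderate, Severe, Life-threatening and Death. Each row has a P-value cell from a chi-square or Fisher test across the four arms of 62, and P below 0.05 is set in bold.
- A further table: "Details of serious AEs and death cases will be summarized and listed in a separate table". No test is named for it.

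The Table 5 footnote says that the entries are numbers of patients. It does not say whether a patient appears once, at the worst grade, or in every grade experienced. The protocol's Data processing and analysis section refers only to the incidence of AEs and adds no grouping of grades. Severity follows CTCAE v5.0.

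**The concern.** The safety question is whether an active arm has more patients with an AE, or more patients with a bad one. Apart from Any, each Table 5 row asks whether the arms have the same proportion of patients at exactly one grade. Two things follow if patients are counted once at worst grade.

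First, an excess of severe-or-worse events is divided among the Severe, Life-threatening and Death rows. Each may be too sparse to show a difference that the same patients would show together. The Any row does not replace a pooled row, because milder events dilute the contrast and it stays flat when events only become worse.

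Second, and conditionally, a patient whose worst event moves up a grade leaves the lower row. A worsening can therefore appear as a significant fall in Mild.

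**Working it through.** **Inputs from the documents.** Four arms of 62 (248 in total), a nominal 5% level, a four-group test per row, and the six Table 5 rows. The SAP states no safety figure. Its one computed figure reproduces and sets the Table 5 denominators: 2/(2.1/3.6)² × 7.9 = 46.43, and 46.43/0.75 = 61.9, or 62 per arm.

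**Assumed inputs.** The documents give no AE rates. I take mild 30% and moderate 10% in every arm, and severe-or-worse 10% on routine care, divided over severe/life-threatening/death as 6/2/2, 4/3/3 or 5/0/5%. Each patient is counted once at worst grade.

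**Row test.** With T patients in a row and x_j in arm j, X² = Σ(x_j − T/4)² / [62 × (T/248) × (1 − T/248)] on 3 df, or its exact analogue with T fixed.

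**Step 1, sparseness.** An expected count of 5 per arm needs 20 patients at that exact grade, 20/248 = 8.1% of the trial. With one patient in each of the other arms, an arm needs 6 for an exact P below 0.05. With two in each, it needs 9.

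**Step 2, power** (20,000 simulated trials per scenario, exact-type test at 0.05; ranges are over the three divisions):

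| Severe-or-worse, routine care v active | Pooled row | At least one of the three split rows | Severe row alone |
|---|---|---|---|
| No effect (10% everywhere) | 4–5% | 7–9% | – |
| 10% v 30%, all three active arms | about 81% | 51–62% | 27–48% |
| 10% v 30%, one active arm only | about 87% | 74–78% | – |
| 10% v 20%, all three active arms | 28–29% | 24–25% | 10–15% |

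The differences between pooled and split rows are 81 − 62 = 19 to 81 − 51 = 30 points in the second line, 87 − 78 = 9 to 87 − 74 = 13 in the third, and 4–5 in the last.

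**Step 3, where pooling loses.** Keep severe at 6% and life-threatening at 2% everywhere, and let only deaths rise, from 2% to 14% in all active arms. The Death row then detects it in 64% of trials and the pooled row in 39%.

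**Step 4, the Mild row.** Fixed counts for illustration (one worse arm v each of the other three, worst-grade counting):

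| Row | Counts | P |
|---|---|---|
| Any | 31 v 31 | 1.00 |
| Mild | 8 v 22 | 0.010 |
| Moderate | 11 v 5 | 0.26 |
| Severe | 5 v 2 | 0.56 |
| Life-threatening | 3 v 1 | 0.73 |
| Death | 4 v 1 | 0.37 |
| Severe or worse (5+3+4 v 2+1+1) | 12 v 4 | 0.031 chi-square, 0.055 Fisher |

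Any and Mild use chi-square, and the single-grade rows from Moderate to Death use Fisher. For the pooled row, T = 24 and Σ(x_j − 6)² = 36 + 3 × 4 = 48, so X² = 48/[6 × (1 − 24/248)] = 8.86. The only bold row in the planned table would be the fall in Mild.

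The pattern depends on the scenario. If AEs only move from mild to moderate (30/10% to 10/30% in the active arms), Mild is significantly lower in 87% of trials, but Moderate is significantly higher in 82%. Mild falls without a significant rise in Moderate in about 15%.

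It also depends on the counting rule. In the fixed-count example, if half of the moderate-or-worse patients also had a mild event and are counted there too, Mild becomes 19 v 26, P = 0.48. If all did, it is 31 v 31, P = 1.00.

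**The case against.** The strongest reply is that this is a matter of table layout. Tabulating by grade is a legitimate choice for secondary safety data in a trial sized on MoCA, and no decision in the plan hangs on these P values. Under worst-grade counting the three high-grade rows do not overlap, so a reader can add them, and serious AEs and deaths are reported separately. The large power gap needs a tripling of severe-or-worse events in every active arm, including an acupressure arm. For a doubling, both layouts are badly underpowered. Most of this stands, and it limits the size of the point. It does not supply the missing comparison: adding three rows gives a count without a test or interval, and the serious-AE table has none planned.

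Three stronger readings are tempting, and the documents do not support them.

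- A reader might infer that a worsening of AEs will pass as a benefit through the Mild row. That requires worst-grade counting, which the SAP does not state; a sentence about tabulating all AEs fits every-grade counting as well. In a simple mild-to-moderate shift the Moderate row usually shows the worsening. The tests have no direction, so the reader would see both sets of counts.
- A reader might infer that serious harm goes unreported. It does not: "Details of serious AEs and death cases will be summarized and listed in a separate table".
- A reader might equate the three top rows with serious AEs. CTCAE grade is severity. The protocol's reporting rules treat seriousness separately, with a category of serious events that are neither fatal nor life-threatening.

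**Conclusion.** The point holds in a limited form. No planned comparison covers severe-or-worse AEs or patients with any serious AE, although safety is a stated aim. Under worst-grade counting and assumed rates of 10% v 30% in all active arms, splitting costs about 19 to 30 points of power and roughly doubles the false-positive chance. The cost is 9–13 points if one arm is worse and 4–5 points for a doubling. Pooling is no guarantee: the fixed-count example is borderline (0.031 or 0.055), and when the excess lies in deaths alone the pooled row does worse, so the Death row must stay.

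The Mild artefact is secondary and conditional on the counting rule. The unstated rule is itself a gap. All AE rates here are assumptions. The efficacy analyses are unaffected.

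**What to change.** In the SAP's Safety outcomes section and Table 5:

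1. State that each patient is counted once, at the worst grade.
2. Compare arms on cumulative rows: any AE; moderate or worse; severe or worse (severe + life-threatening + death); any serious AE, defined separately from severe; and death.
3. Keep the exact-grade counts beside them as description, without P values.

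The cost is SAP wording and one changed table shell. Severity is already recorded for each AE. Seriousness is not among the listed per-event fields, but serious events must already be identified for expedited reporting and for the planned separate table, so the team should confirm that the record form captures it. The downside is that a pooled row mixes grades and loses some power when harm is confined to one grade. Keeping Death as a compared row and showing the exact-grade counts limits this.
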